3.3. Data and Safety Monitoring Plan

3.3.1 Safety Monitoring Framework

Data and safety will be monitored on several levels. At the first level, the Principal Investigator, [name], will have ultimate responsibility for reviewing conduct of the study and data produced from it, including the reporting of any adverse events to the IRB of the New York State Psychiatric Institute (single IRB of record). At the second level, the project will use a Performance and Safety Monitoring Board (PSMB), as described below. Adverse events and results of PSMB reviews also will be reported to the NIDAs program officer, as described below. All research protocols will be approved by New York State Psychiatric Institute IRB and NIDA.

Data to be collected and monitored includes demographics, a variety of attitudinal/beliefs toward COVID-19 risk and infection transmission, and organizational functioning via surveys, focus groups and medical records on COVID-19 test dates, location of testing, and results drawn from Healthix, the large public NYC based health information exchange (HIE).

3.3.2 Data Monitoring

Interim Analysis Plans: The DSMB will review safety reports quarterly (see below). More frequent meetings will be scheduled if indicated by interim findings. A written summary will be submitted to the IRB following each meeting.

The data analyst will conduct interim analyses quarterly to verify that recruitment is consistent with projections. To support ongoing quality assurance and uniformity in data collection, interim analyses will also be conducted to examine patterns of missing data from surveys. Analyses to assess the psychometric properties of the measures will be conducted following the first implementation cycle. These data will be made available to the DSMB. In addition, data from the Site Recruitment Monitoring Form will be made available to the DSMB for monitoring of recruitment and participation rates for all assessments, as well as refusal and attrition rates and study progress.

Stopping Rules: This study will be stopped prior to its completion if: (1) the intervention is associated with adverse effects that call into question the safety of the intervention such as increased rates of COVID-19 infection; (2) difficulty in study recruitment or retention, or enrollment of participants will significantly impact the ability to evaluate the study endpoints; (3) any new information becomes available during the trial that necessitates stopping the trial; or (4) other situations occur that might warrant stopping the trial.

3.3.3 Management and Reporting of Adverse Events (AEs), Serious Adverse Events (SEAs) and Unanticipated Problems (UP).

This study will use the NIH Reportable Events Policy definition of Adverse Events (AEs), Serious Adverse Events (SAEs) and Unanticipated Problems Involving Risk to Subjects (UP).

We will define and measure risk as indicated in the table below.

Table 3.3a. Method of Ascertainment of Serious and Adverse Events, and Unanticipated Problems for STAFF (Sample 2)

oh

Reportable Event	What they are in the study	Method of Ascertainment	Reporting Requirements		
			IRBs	PSMB	NIDA PO
Death	- Employee/staff death during study operations	We will ask peer supervisors, site coordinators and agency leadership to report any deaths as soon as they learn of them.	ASAP, but no later than 3 working days	Immediately	ASAP, but no later than 3 working days
SAEs	- Employee injury requiring hospitalization during study events	We will monitor these directly at study events that research staff are present at, and ask employee leadership/staff/peers to report them if we are not in attendance.	ASAP, but no later than 3 working days, regardless of whether SAE is study-related	ASAP, but no later than 3 working days	ASAP, but no later than 3 working days
Other AEs	- Employment discipline for improper handling of participant	We will document these events, when we learn of them, per peer supervisors/CBO	Annually. Note that documentation of these events	Tri-Annually	Tri-Annually

	
 - Employee distress related to managing a participant positive for COVID-19 - Staff breach of confidentiality 	leadership and peer to self-report.	must also indicate whether they are thought to be study related and why or why not.		
Unexpected AEs	An AE whose nature, severity, or frequency has not previously been identified. Also includes any adverse event that results in a participant's withdrawal from the study; or is due to a deviation in the research protocol	We will ask all study staff to raise concerns that they have directly via email.	ASAP, but no later than 5 working days.	Immediately if related to study. Tri-Annually if not related to study.	Immediately if related to study. Tri-Annually if not related to study.
Unanticipated Problems that are Not AEs	Incidents or outcomes that occur during human subjects research that are not AEs, but that involve social or economic harm (instead of physical or psychological harm), or are problems that place subjects or others at increased risk of harm, but where no harm occurs.	We will ask all study staff to raise concerns that they have directly in-person or via email.	ASAP, but no later than 5 working days. If MPIs deem the event likely to affect participants, it must be reported to the IRB immediately.	Immediately if related to study. Tri-Annually if not related to study.	ASAP, but no later than 3 working DAYS
Protocol Violations	Deviations from the IRB-approved study procedures, as outlined in the Protocol Summary Form that has received review and approval by	We will meet internally once a week to review study activities and, if we determine we have violated our protocol, we will record the incident	Within 2 weeks of staff becoming aware of the violation; no later	Annually	Annually- Should be included in the full data report

	the IRB. A significant protocol deviation would be a deviation that increases the risk to participants or others, or decreases the potential benefits of the study, undermines the scientific integrity of the study, or occurs more than once	and remediate immediately.	than 5 days if the violation results in an unanticipated problem.		
IRB-or-PSMB determined suspension	Any suspension or termination of approval must be reported including a statement of the reason(s) for the action.	We will comply with IRB, DSMB, and NIMH procedures and guidance.	3 business days	3 business days	3 business days

Table 3.3b Method of Ascertainment of Serious and Adverse Events, and Unanticipated Problems for TESTING PARTICIPANTS (Sample 1)

Reportable Event	What they are in the study	Method of Ascertainment	Reporting Requirements		
			IRBs	PSMB	NIDA PO
Death	
 - Suicide event - Non-suicide death during study operations 
 - Death by overdose 	
Via peer supervisors, site coordinators and agency leadership self- report any deaths as soon as they learn of them.
 
Note: follow-up appointment status update
	ASAP, but no later than 3 working days	Immediately	ASAP, but no later than 3 working days
SAEs	
 - Suicide attempt following disclosure of suicidal ideation during assessment - Participant transport to 	Participants who endorse suicidal ideation and present as high-risk after emergency protocol is enacted may be referred to emergency services	ASAP, but no later than 5 working days, regardless of whether SAE is study-related.	ASAP, but no later than 3 working days	ASAP, but no later than 3 working days

	emergency services Non-lethal Overdose	by study staff if applicable. We will follow-up with participants who initially endorse suicidal ideation and are determined to be low-risk 3-7 days from their initial visit to assess suicidal risk. If participant self-reports suicide attempt we will document the SAE and report it as required, and link participant to mental health services.			
Other AEs	- Distress related to a COVID-19 positive test - Remission (substance use) following recruitment - Coercion into participating by peer recruit - Breach of confidentiality	We will ask all study staff to raise concerns that they have directly in-person or via email and we will also ask about any potential problems during our check-in calls with CBO leadership and peer supervisors.	Annually. Note that documentation of these events must also indicate whether they are thought to be study related and why or why not.	Tri-Annually	Tri-Annually
Unexpected AEs	An AE whose nature, severity, or frequency has not previously been identified. Also includes any adverse event that results in a participant's withdrawal from the study; or is due to a deviation in the research protocol	We will ask all study staff to raise concerns that they have directly in-person or via email and we will also ask about any potential problems during our check-in calls with CBO leadership and peer supervisors.	ASAP, but no later than 5 working days.	Immediately if related to study. Tri-Annually if not related to study.	Immediately if related to study. Tri-Annually if not related to study.

Unanticipated Problems that are Not AEs	Incidents or outcomes that occur during human subjects research that are not AEs, but that involve social or economic harm (instead of physical or psychological harm), or are problems that place subjects or others at increased risk of harm, but where no harm occurs.	We will ask all study staff to raise concerns that they have directly in-person or via email and we will also ask about any potential problems during our check-in calls with CBO leadership and peer supervisors.	ASAP, but no later than 5 working days. If MPIs deem the event likely to affect participants, it must be reported to the IRB immediately.	Immediately if related to study. Tri-Annually if not related to study.	ASAP, but no later than 3 working days
Protocol Violations	Deviations from the IRB-approved study procedures, as outlined in the Protocol Summary Form that has received review and approval by the IRB. A significant protocol deviation would be a deviation that increases the risk to participants or others, or decreases the potential benefits of the study, undermines the scientific integrity of the study, or occurs more than once	We will meet internally weekly to review study activities and, if we determine we have violated our protocol, we will record the incident and remediate immediately.	Within 2 weeks of staff becoming aware of the violation; no later than 5 days if the violation results in an unanticipated problem.	Annually	Annually-Should be included in the full data report.
IRB-or-DSMB determined suspension	Any suspension or termination of approval must be reported including a statement of the reason(s) for the action.	We will comply with IRB, DSMB, and NIMH procedures and guidance	3 business days	3 business days	3 business days

3.3.3.1. Protocols for preventing/mitigating specific risks. Participant distress will be managed by supervising clinical staff at either Argus or Alliance. Should additional assistance be required, supervising clinical personal within either agencies will contact the PI [name], a licensed clinical psychologist, who will provide further assistance. Risks associated with breaches of confidentiality and resulting retribution due to staff responses are a concern. Breaches of confidentiality are unlikely, given the PI's commitment to and experience in maintaining participant confidentiality. Breaches are not anticipated at NYSPI/CUMC offices, because as a research facility, standards for maintaining participant confidentiality have been rigorously maintained since we began research. Breaches might nonetheless occur. During the informed consent process, participants will be told of the confidentiality procedures that are in place, but will be informed that a breach is still possible, however rare, despite these procedures. Should a breach occur, four steps will be taken. First, the participant will be informed as to the nature of the breach, and its possible ramifications. Second, the PI will immediately notify the NIDA Project Officer and the IRB. Third, the PI will review existing confidentiality safeguards to determine why and how the breach occurred (outlined below). Fourth, the PI will halt data collection until such time that the IRB can review existing procedures as to their quality and completeness. The following steps are in place to guard against breaches of confidentiality and to protect confidentiality of research data:

- 1) Provisions in all protocols will be made to ensure that a) all participants review IRB approved consent (information) forms, b) all surveys are conducted on-line via secure login and data held on a secure server or conducted via pen/paper at the participants choice of location and pace , c) no personal identifying information is collected on data forms, d) all administrative data collected are stripped of identifying information, e) no public data files contain any HIPPA identifiers, f) participants understand the voluntary nature of study participation, g) all data collected are kept in a secured, locked area with access by only certified research staff, and h) all approvals and documentation from the IRB and other approval entities are easily accessible by the PIs and research coordinators.
- 2) All staff in focus groups, or any study related meetings, will be asked will be asked to respect the confidentiality and privacy of the other participants
- 3) The research data will be collected electronically (Healthix, participant survey data, recording of coupons). Only trained researchers will be involved in data extraction efforts and delivery of survey forms to study sites. All project staff are required to obtain the NIH web-based certification for protection of human subjects and to sign statements of confidentiality. All staff will be aware of the NYSPI/CUMC confidentiality agreements, the NIH Confidentiality Certificate, and their responsibilities regarding the Certificate's special protections. Staff members that leave the project will be reminded of their continuing obligations to maintain confidentiality. The team has internal procedures to ensure that all staff are aware of federal and state statutes and regulations regarding confidentiality of data.
- 4) Completed surveys will be downloaded from the web to a secure drive or hand delivered or mailed securely to NYSPI/CUMC offices. Research questionnaires will be coded with a unique number only. The unique ID number will appear on all records in lieu of personal names or other identifying information. Separate follow-up locator forms with identifying information will be digitally stored on password protected servers at NYSPI/CUMC offices. Unique file numbers linking questionnaires with locator forms and identifiers will be stored on the PIs computer in a password protected file NYSPI/CUMC servers. Data from agency records (Healthix) will be provided to the NYSPI team via secure data transfer. Any identifiable data will be removed from these data before transferring them to project files; the unique ID number associated with the individual will also be used exclusively with these data. The research team will not release any individually-identifiable data back to the agencies involved in the research.
- 5) Any data entry and verification/clean will occur on secure NYSPI/CUMC servers under the supervision of the data manager. Computerized copies of research data will be kept on a password protected hard drive maintained by the Data Manager; back-up copies will be kept in locked files at the NYSPI/CUMC offices. The project statistician, [name], will ensure that it will not be possible to reconstruct participant identities from the data collected. Security of the data is maintained through the use of secure servers and regular backups, including off-site storage. On a quarterly basis, the PI will meet with the project

staff to review and monitor data safety and monitoring procedures. The PI provide the logistical and operational support for DSMB meetings.

3.3.3.2 Protocol for identifying and tracking individual staff SAEs, AEs and UPs. Adverse events may be ascertained (1) by direct report of a participant during a planned research visit or activity, (2) interaction with research staff, or (3) as reported by agency leadership to research staff. All events, regardless of how ascertained, will be recorded by the research Project Director in an AE/SAE log as they occur. The master copy of the log will be updated and stored on RFMH/CUMC secure servers. Upon learning of an SAE, AE or UP, research staff will be instructed to inform the PI as soon as possible (but within 48 hours of discovery) and get the necessary information for completing the Negative Event Incident Report. The PI reviews the Negative Event Incident Report and adds additional information as necessary, and submit it to the DSMB (See below), the NIDA Program Official, and to the IRBs as required. The PI will ensure that SAEs AEs and UPs are followed until a final disposition of the event is made and a final report on the SAE, AE or UP is filed with the DSMB. If a study participant withdraws from the study or the PI/co-Is decide to discontinue a participant due to an SAE, the PI will monitor the participant until (1) a resolution is reached; (2) the SAE is determined to be clearly unrelated to the study intervention; or (3) the SAE results in death. Using the rating system for SAEs , the PI will evaluate each SAE or unanticipated AE to determine whether it is related to the study, whether it affects the risk/benefit ratio of the study, and whether modification to the protocol or the consent form is required.

3.3.3.3 Protocol for reporting of adverse events. Events that are serious or unexpected must be recorded using the ethics committees' SAE/Unexpected Event forms and submitted to the New York State Psychiatric Institute (NYSPI) IRB within 5 working days from the time that research staff becomes aware of the SAE or AE (See Table). The PI must review the SAE form and sign and date the form; the PI will be responsible for informing the NYS Psychiatric Institute (Columbia University) IRB and the NIDA Program Officer.

Regular monitoring of the study will be undertaken by the PI and other research designated staff (e.g. PD) every three months to ensure that all study procedures are being adhered to, that record-keeping is accurate, and that adverse events are being identified and followed up. Below we summarize types of events and reporting requirements.

3.3.4 DSMB Project Review. While the PI ([name]) will have ultimate responsibility for reviewing conduct for the study and data emanating from it, including the reporting of any adverse events to the Institutional Review Boards of Columbia University/the New York State Psychiatric Institute (NYSPI), the Data Safety Monitoring Board as assembled by the CDCC through the RADx-UP consortium will meet to review this project at least once each year in addition to reviewing quarterly data safety reports prepared by the research. After the meeting, the DSMB members present written feedback to the research. This feedback will be shared with NIDA program officers, and with the respective IRBs.

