Staff, credible messenger and CAB member focus group. At the end of Phase 2, interested agency staff, credible messengers and CAB members will be invited to participate in two focus groups to understand staff attitudes and perspectives on integration of each recruitment strategy and COVID-19 testing and related services into ongoing agency workflow; changes in job role, performance, or load. Staff focus groups will be run separately from CM/CAB member group and will be conducted in a private room at the home agency. The focus groups will each take approximately 1 hour to complete. Focus groups will be digitally recorded and transcribed, with the participants' consent, to facilitate the coding and analysis of these data.

Process measures: During Phase 2, participants recruited via chain-referral or credible messengers will complete a process measure, created for the study, consisting of a brief set of questions to monitor for potential ethical concerns arising among participants during the recruitment process. These questions will be defined during the intervention development process in Phase 1 and will address issues related to any unwanted disclosure of sensitive information, perceived or actual coercion or other potential psychological harms. Staff and CMs will complete a series of checklists capturing fidelity and feasibility of either recruitment method and delivery of the on-site testing.

Biological samples: During Phase 2 participants recruited via chain-referral or credible messenger will be asked to provide biological samples for COVID-19 testing, namely anterior nasal swabs for the BD Veritor™ SARS CoV 2 and Cepheid Xpert SARS CoV 2 testing platforms. Further details of the testing process can be found in Section 3.3 Testing Capacity.

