There may also be several privacy-related and psychological risks associated with this study: (1) the risk a participant may reveal sensitive information about themselves; (2) the risk a participant may feel coerced into participating or may attempt to coerce others into participating during peer-recruitment; (3) the risk of contact between participants in treatment/recovery for substance use disorders and their peers who are actively using substances; (4) the risk a participant may reveal sensitive information about individuals who have not consented to be in the study; (5) the risk of an unintended breach of confidentiality; and (6) the risk of discomfort in participating in study procedures. Each of these risks is discussed below:

- 1) Participants may reveal sensitive information in this study regarding their substance use, mental health, motivation to receive treatment for substance use disorders, and relationships to members of their social networks, perceived risk of infection of COVID-19, risk reduction behaviors and social and socioeconomic impact of COVID-19. Interviews will take place in private offices at clinical sites. For all interviews, it is possible that subjects may experience feelings of distress when answering questions concerning these topics. Furthermore, some participants will be asked to recruit their peers for participation in the study. In

doing so, it is possible that sensitive information about the participant may come up as a topic of conversation with those they are attempting to recruit. This may cause feelings of distress if unexpected or unwanted.

- 2) Participants may also feel coerced into participating, believing that their decision to participate (yes/no) may affect, either positively or negatively, their ability to receive COVID-19 testing or other services. Conversely, it is also possible that during the recruitment process, participants or credible messengers might attempt to coerce others to enroll in the study.

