- 3) Some participants may be engaged in treatment for substance use disorders or otherwise attempting to abstain from substance use (i.e. in recovery) at the time they engage in peer-recruitment. During the study, participants will be asked to focus recruitment on individuals they believe to be actively using substances. Therefore, it is possible that participants in recovery will have contact with peers who are actively using substances, which they would not otherwise have. Such contact may cause participants to experience cravings to return to active use.
- 4) Participants may reveal sensitive information about individuals who have not consented to participate in the study in one of two ways: a) while completing social network inventories, participants will be asked sensitive questions about their social network contacts who, in most cases, will not themselves be enrolled in the study; and b) during peer-recruitment, participants may ask social contacts about their substance use behavior, treatment access and COVID-19 risk and testing behaviors.
- 5) Staff and credible messenger participants will be asked to complete questionnaires about their organization's mission, structure, culture/climate, resources. Participants will not be asked questions that would put them at risk of criminal or civil liability or damage to financial standing, employability or reputation. Some organizational culture and climate questions, although not structured or intended to do so, could invite negative opinions critical of leaders, supervisors and/or coworkers and the risk of accidental disclosure of their responses may create discomfort for respondents or may increase the risk of repercussions to participants from supervisory staff who may be present in the focus group. In addition to being asked to complete surveys and/or to be interviewed, the work-related interactions of staff participants may be observed and other data related to quality assurance (e.g. activities that occur within Interagency work group meetings) will be collected.

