- 2) The risk a participant may feel coerced into participating or may attempt to coerce others into participating during peer-recruitment: The utmost care will be taken to ensure that participants do not feel coerced in anyway and that they understand taking part in the proposed studies are voluntary. Specifically, during informed consent of potential participants the research staff will emphasize that their choice whether or not to be in this study will not impact either their own ability the ability of those who recruited them to receive services at either Argus or Alliance. Though enrollment will occur in private offices located at Argus and Alliance, agency staff will not be present for the informed consent process. Furthermore, research staff will make explicitly clear that the research study is not a part of usual care at those clinical sites.

The prospect of coercion by study participants during peer-recruitment has long been a consideration for studies using respondent-driven sampling (RDS), which serves as the basis for the peer-recruitment protocols planned for the proposed study. However, in a comprehensive review of ethical and regulatory concerns related to the use of RDS in scientific research, the authors found that the empirical literature, concerns related to coercion by study participants are offset by appropriate safeguards, including: a) limiting amount of reimbursement per peer-recruitment coupon; b) limiting the maximum number of coupons per participant; c) asking individuals redeeming coupons about perceived coercion; and d) having research staff obtain informed consent for new peer-recruits.¹⁰

- 3) The risk of contact between participants in treatment/recovery for substance use disorders and their peers who are actively using substances: As with the risk of disclosures above, the risk of cravings to return to active substance use among participants in recovery will monitored through process measures in Phase 2. Similarly, content for the recruitment strategies will also be created in Phase 1 that helps to help participant recruits anticipate, mitigate and manage potential cue-associated cravings resulting from peer-recruitment efforts.

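### Table 3.3b lists substance-use remission as an adverse event, which contradicts the protocol's stated risk of cravings to return to use

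*Combined protocol and SAP*

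**What the plan says.** Section 3.3.3 gives the event tables operative force: "We will define and measure risk as indicated in the table below". Table 3.3b applies to testing participants (Sample 1). Its Other AEs row has four entries: distress over a positive COVID-19 test, "Remission (substance use) following recruitment", coercion by a peer, and breach of confidentiality. Events in this row go to the IRB annually and to the monitoring board and the NIDA program officer three times a year. They are found through concerns raised by study staff and check-in calls with agency leadership and peer supervisors.

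The risk list in Section 3.1.1(b) includes "the risk of contact between participants in treatment/recovery for substance use disorders and their peers who are actively using substances". Item 3 of that section states the consequence: "Such contact may cause participants to experience cravings to return to active use". Item 3 of Section 3.1.2(b) then says that "the risk of cravings to return to active substance use among participants in recovery will monitored through process measures in Phase 2". The process measure is described in Section 3.1.1(b) under Phase 2. Its questions are to be settled in Phase 1 and "will address issues related to any unwanted disclosure of sensitive information, perceived or actual coercion or other potential psychological harms".

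**The concern.** An adverse-event table tells staff what to write down. Here the named event is a favourable outcome, and the harm that the risk sections anticipate is not named. Taken literally, the row would bring remissions to the monitoring board as adverse events and give staff no prompt to log a relapse or cravings.

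This matters for the comparison because the risk is uneven between strategies. Among testing participants, only those in chain referral are asked to recruit peers (Section 2.5). Seeds are clients of the two agencies, which specialize in substance use treatment (Section 3.1.1(a)), and Section 3.1.1(b) expects some recruiters to be in treatment or recovery. The plan is to carry the efficacious strategy forward and scale it up (Section 4.8). A harm that falls mainly on one strategy should be countable before that choice is made. It should also be countable for the safety ground in the stopping rules of Section 3.3.2.

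**Working it through.** The point involves no figure, so the check sets the texts side by side.

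1. **Direction of the event.** The table names remission. Sections 3.1.1(b) and 3.1.2(b) name cravings to return to active use. These point in opposite directions. Remission is not defined in the body text or in the abbreviations and special terms, so no local definition turns it into a harm.

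2. **Company it keeps.** The other three entries in the cell (distress, coercion, breach of confidentiality) are all harms. This suggests that a harm was meant, but not which one: cravings, return to use and relapse would all fit.

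3. **Row-by-row search of Table 3.3b for the harm.**
   - Death: suicide, non-suicide death, and "Death by overdose". This covers only a fatal consequence of return to use.
   - SAEs: suicide attempt after disclosed ideation, transport to emergency services, and "Non-lethal Overdose". This covers return to use that ends in overdose or transport.
   - Other AEs: the remission entry and the three harms above.
   - Unexpected AEs: events of a nature, severity or frequency not identified beforehand, plus any adverse event that leads to withdrawal or stems from a protocol deviation. A risk the protocol itself foresees fits the first clause poorly. The other two clauses catch only some cases.
   - Unanticipated problems that are not AEs: social or economic harm, or raised risk without harm. Relapse and cravings are not named.
   - Protocol violations and suspension of approval: not relevant.

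   Rows that name relapse, return to use or cravings: 0 of 7.

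4. **Is the harm caught elsewhere?** Section 3.1.2(b) assigns cravings to the Phase 2 process measure. The description of that measure in Section 3.1.1(b) names disclosure, coercion and other psychological harms. It names neither cravings nor return to use, although the last category could include cravings. The ascertainment column of the Other AEs row does not mention the measure, so the documents show no link between that measure and this row.

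5. **Size.** The documents give no rate of relapse or cravings, and no number of recruiters in recovery. No count of affected events can be derived.

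**The case against.** The strongest reply is that this is an obvious slip. A sensible reader who sees remission among three harms, tied to recruitment, will take it as relapse. Nothing in the documents shows that staff reported remissions or left relapses unlogged. That reply stands as a limit on consequence: what would be logged wrongly is conditional on a literal reading. It does not make the definition right, because a reporting definition should not depend on each staff member making the same guess.

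A reader might go further and infer that every return to use short of overdose falls outside the table. The documents do not support that. Section 3.3.3 also adopts the NIH definition of an adverse event, the SAE row includes emergency transport, the Unexpected AEs row takes in events leading to withdrawal, and staff and agency leads may raise any problem. Section 3.3.3.2 also provides for logging events from any source, although its heading refers to staff events.

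A reader might also infer that the protocol states return to use itself as the risk. It does not: both sections say cravings, one step short of it. Remission matches neither.

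Finally, the anticipated risk is not ignored. The process measure is planned, and Phase 1 content is meant to help recruiters handle cravings. Only some participants are in recovery, and all must report substance abuse in the past six months. These points narrow the reach of the error and leave the contradiction in place.

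**Conclusion.** Wrong as written. The Other AEs row of Table 3.3b names an improvement as a reportable adverse event, contrary to the risk stated in Sections 3.1.1(b) and 3.1.2(b), and no row names relapse, return to use or cravings. The harm is not wholly unmonitored: overdose and emergency transport are listed, and other cases have general or discretionary routes. The effect is confined to safety reporting. Sample size, power and the primary analysis are untouched, and the number of events affected is unknown.

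The conclusion assumes that remission carries its ordinary meaning, since the protocol gives no other, and that staff work from the table, as Section 3.3.3 says. That remission was a slip for relapse is likely, but it is an inference.

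**What to change.** Reconcile the row with item 3 of Section 3.1.1(b) and item 3 of Section 3.1.2(b). Replace the word remission with the harm the sponsor intended and define it; examples are return to substance use, or cravings to return to use, following recruitment. Cite the Phase 2 process measure in the ascertainment column of the same row, and confirm that its questions cover the defined event.

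The cost is a few words in one table row, and the process measure is already planned. Section 2.6 gives the status as not recruiting and Table 1 shows 486 participants, so the sponsor should also check how events under this row were logged. The label should be corrected before safety results are posted or the protocols are shared under Section 4.8.
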